6.1.1 Pre-Enrollment (S -0)

Activity 1: Practitioner completes pre-intervention diagnostic vignette

6.1.2 Enrollment/Baseline (S0= Day 0)

Activity 2: Practitioner and office staff training

6.1.3 Pre-intervention Stage (S1)

(*Pilot Phase: Complete within approximately 2 weeks following S0 Full study*: Complete within approximately 6 weeks following S0)

- Activity 3: Pre-intervention patient data collection procedures lasting approximately one week in the pilot phase and four weeks in the full study (see Section 6.2 below)
- Activity 4: Practitioner is randomized into one of three arms (no device, DIAGNOdent, Spectra).

6.1.4 Intervention Stage (S2)

(Pilot Phase: Complete within approximately 2 weeks + 1 week following S1 Completion

Full Study: Complete within approximately 8 + 2 weeks of S1 Completion)

Activity 5: If the practitioner is randomized to the device arm, then he or she will undergo device familiarization. The device familiarization will include practitioners viewing the manufacturer's instructions and familiarizing themselves with the devices through unsupervised clinical use with patients prior to using the device for study data collection.

Activity 6: Patient data collection procedures (see Section 6.2 below)

6.1.5 Post-Intervention Stage (S3)

(*Pilot Phase: Complete within approximately 1 week following S2 Completion Full Study: Complete within approximately 2 weeks of S2 Completion*)

Activity 7: Practitioner completes the post-study vignette; and

Activity 8: Practitioner completes the post-study questionnaire

6.2 Patient:

6.2.1 Screening

A potential subject may be recruited at any dental visit, not just examination or recall visits. During the course of a dental visit, when it is determined that a patient has an SOCL (using their usual methods for determination) and may be eligible for study participation, the designated office personnel will introduce the study to the patient and will ascertain that inclusion criteria are met. Enrollment, examination, and treatment may occur during the same dental visit at which eligibility was confirmed.

6.2.2 Pre-intervention Stage Enrollment/Pre-Intervention

For patients who express interest in participating in the study, a designated office individual will execute the consent process with the patient and ensure that the consent document has been executed. It is anticipated that in most cases this will be the dentist.

Screening Failures: If the patient expresses a verbal refusal to participate, this will be noted in a CRF/log; in such cases, the informed consent process will not be followed and the patient will be treated as a failure to provide consent. If the patient does not express a negative disposition to participation, the informed consent process will be carried out.

- Verify inclusion criteria;
- Obtain and document consent from potential participant;
- Practitioner record results of dental examination; and
- Practitioner record results of dental treatment.

6.2.3 Intervention Stage Enrollment/Baseline

- Verify inclusion criteria;
- Obtain and document consent from potential participant;

- Practitioner records results of dental examination, during which the device will be used (if in the device arm); and
- Practitioner records results of dental treatment.

7 STUDY PROCEDURES/EVALUATIONS

7.1 Study Procedures/Evaluations

Practitioner: The practitioner will complete a pre-study vignette online. After the study is complete, he/she will also complete a post-study vignette and questionnaire. For the pre-and post-study vignettes, practitioners will be given scenarios with photos. They will be asked to indicate how likely they would be to recommend a variety of treatments based on four cues: color, luster, and roughness of the lesion and caries risk characterization.

Patient: Once a patient has consented to participate and is enrolled, assessments are performed for the study based upon clinical examination findings and recorded on data collection forms. The forms will require the following information:

Provided by patient

• Subject age, sex, race, and ethnicity

Provided by practitioner

- Subject caries risk information;
- Clinical description of the lesion;
- Description of treatment provided;
- Clinical description of opened lesion, if operative intervention undertaken; and
- Practitioner's assessment of patients' caries risk category

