2.2 Rationale

The overall significance of the study is in determining whether the use of caries detection devices increases congruence with current best evidence. Based on three studies done in the 2005-2012 cycle of the former Dental PBRN^{3,13-15}, for many dentists the uncertainty leads to surgical treatment when it is possible that non-surgical treatment could effectively stop caries progression and at the same time spare tooth tissue.

The nation's network offers an excellent opportunity to conduct a study that evaluates the outcomes associated with the use of two of the most popular of the diagnostic devices. The study will determine whether dentists who use a device treat SOCLs surgically more often, with the same frequency, or less frequently, than dentists not relying on a device. The study will also determine -- among those SOCLs that are opened -- whether the proportion of lesions that extend into the dentin when dentists are using a device is more than, the same, or less than when no device is used.

Additionally, pre- and post-study diagnostic vignettes that simulate the decision making process will afford an understanding of what cues in the lesion presentation are influential in dentists' management decisions, and to what extent information provided by a diagnostic device reinforces or overrides those cues. Because the vignettes are designed to simulate the clinical situations for which data collection will occur, their fidelity in predicting practitioners' treatment decisions will also be assessed, providing a unique and needed insight into their utility for future studies of diagnostic decision-making. Finally, dentists' assessments of the utility of the devices in their practices will also be gained. The overall goal is to assess the contribution of these devices in dentists' decision-making processes surrounding SOCLs, an assessment that has not yet been attempted despite their growing popularity.

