3 OBJECTIVES

3.1 Study Objectives

Primary: The primary objective is to quantify the difference in proportion of SOCLs treated operatively when a diagnostic device is used compared to when one is not used and to quantify the difference in proportion of SOCLs treated surgically that extend into dentin when a diagnostic device is used compared to when one is not used.

Secondary: The secondary objectives are to identify the clinical characteristics of SOCLs that best predict caries that extends into dentin, to determine whether the principal factors used by participating practitioners in managing SOCLs change when a caries detection device is employed, and to obtain practitioners' assessments of the utility of the devices in their practices. Because the vignettes are designed to simulate the clinical situations for which data collection will occur, their fidelity in predicting practitioners' treatment decisions will also be assessed, providing a unique and needed insight into their utility for future studies of diagnostic decision-making.

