7.2 Questionnaire Administration

Practitioner: Practitioners will be directed to a secure website to complete the pre-and poststudy vignettes. After providing consent, practitioners will observe 16 unique patient profiles consisting of a text vignette and photo of a SOCL. The 16 profiles have been shown to be a valid and reliable approach to examining how practitioners use patient demographic cues to make lesion management decisions. For each patient profile, practitioners read a clinical vignette that describes the patient as having 4 various cues (color, luster, roughness of the lesion and caries risk characterization).

All practitioners will complete a post study questionnaire. This will also be done electronically similar to the vignettes. Practitioners randomized to the device arm will complete a post-study questionnaire on the utility and value of their device in addition to the pre-and post-study vignettes while practitioners on the no device arm will complete a post-study questionnaire on the vignette and participation in the study.

Patient: The patient will complete the demographics form.

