To determine whether the principal factors used by participating practitioners in managing SOCLs change when a caries detection device is employed, the Lens model analytic approach will allow for the determination of the unique contribution of each of the 4 principal features (color, luster, roughness, risk) to the treatment decision. An overall significance of each equation and the variance it accounted for will be determined for the decision to surgically intervene and the confidence of that decision. These represent the main a priori hypotheses from the decision study (vignette) portion of the project. In addition to those a priori hypothesized analyses, a number of more exploratory analyses are possible within the Lens model approach. This could include demographic characteristics of the dentists (age race, sex, experience in practice etc.). These individual difference variables would be included in the nomothetic analyses only. Finally, the similarity of treatment predictors will be examined across the in vivo and vignette portions of the study as an initial cross validation of the two approaches. We will examine the concordance rates and/or correlations between number of decisions to intervene across the two portions of the study and across groups (device trained vs. no device).

The proposed sample size, developed in the previous section was developed using conservative assumptions regarding effect size and potentially missing data. The study is anticipated to provide adequate statistical power even if approximately 20% of observations have missing values for some variables, depending on the differences and level of ICC that are actually observed in the study. Issues regarding missing values are presented in further detail in the Appendix E.

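### The four-cue vignettes cannot show how a device reading is weighed against the other cues, and the stated vignette tests do not set the pre-to-post shift against the no-device arm

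*Protocol*

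**What the plan says.** One secondary objective in Protocol Section 3.1 is "to determine whether the principal factors used by participating practitioners in managing SOCLs change when a caries detection device is employed". Section 2.2 goes further and says the vignettes will also show "to what extent information provided by a diagnostic device reinforces or overrides those cues".

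On content, Section 7.1 says practitioners rate how likely they are to recommend treatments "based on four cues: color, luster, and roughness of the lesion and caries risk characterization". Under Section 7.2, "practitioners will observe 16 unique patient profiles consisting of a text vignette and photo of a SOCL", and the same four cues are listed again. Sections 4, 7.1 and 7.2 have practitioners in every arm complete both the pre-study and the post-study round.

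On analysis, Section 11.3 uses a Lens model for "determination of the unique contribution of each of the 4 principal features (color, luster, roughness, risk) to the treatment decision". It continues: "An overall significance of each equation and the variance it accounted for will be determined", for the decision to intervene surgically and for confidence in that decision. Of these it says: "These represent the main a priori hypotheses from the decision study (vignette) portion of the project".

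The Précis says that differences between pre- and post-study vignette responses will indicate which parts of decision making the devices modified. Section 3.2.2 describes assessment before and after device use for those in a device arm.

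**The concern.** There are two linked problems.

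The first is content. Section 2.2 promises a result about how device information competes with the visual and risk cues, but neither description of the vignettes includes any device information. Respondents cannot reveal the weight they give to something they are not shown.

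The second is inference. What the vignettes can measure is a shift in the four cue weights between rounds. The tests named as the main a priori hypotheses examine each equation on its own. The before/after framing elsewhere attributes change to the device without reference to the no-device arm. Practitioners in all arms repeat the exercise after weeks of recording the lesion features that the vignettes use, so some change is plausible with no device at all. Randomisation supplies the control for this, but the stated vignette tests do not use it.

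**Working it through.** The protocol gives no sample size, power or effect size for the vignette aim, so there is no figure of its own to reproduce.

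**Step 1. Is a device reading present?**

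| Place | Content |
|---|---|
| Section 2.2 | Promises the effect of device information relative to the cues |
| Section 7.1 | Four cues: color, luster, roughness, caries risk |
| Section 7.2 | The same four cues |
| Section 11.3, Lens model | Weights for the same four features |

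Neither of the two vignette descriptions includes a device reading, and the model has no device term. The clinical data items listed in Sections 3.2.2 and 7.1 mention aids to diagnosis but no device reading, so they do not clearly supply one either.

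**Step 2. What do the stated tests measure?** For one equation, overall significance asks whether the four weights are jointly zero, and explained variance asks how much they account for together. Neither is a test of change. With uncorrelated, standardised cues, explained variance is the sum of the squared weights. If two cues exchanged weights between rounds, it would stay the same although the factors used had changed.

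**Step 3. Which comparison isolates the device?** Let R be the retest change in a cue weight shared by all arms, and D the additional change from device experience.
- Post minus pre, device arm: R + D
- Post minus pre, no-device arm: R
- Difference between arms: D

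A before/after comparison within the device arms estimates R + D. The only arm comparison attached to the vignettes in 11.3 concerns agreement between vignette and clinical decisions. The comparison of mean changes among groups in Appendix E is exploratory and concerns clinical rates of operative treatment, not cue weights.

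**Step 4. How stable are single-dentist equations?** Residual degrees of freedom are 16 profiles − 4 cues − 1 intercept = 11. If a cue has power p in each round and the rounds are independent, it changes significance status with probability 2p(1 − p) when nothing has changed. The protocol gives no p. Assuming p between 0.3 and 0.7, this is 0.42 at either end and 0.50 at p = 0.5. Changes of significance in individual equations therefore say little.

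**Step 5. What could the between-arm contrast detect?** The planned data are 90 practitioners × 16 profiles × 2 rounds = 2,880 responses. These are clustered, so the practitioner is the unit for the contrast. With n practitioners per arm and the change in one cue weight in SD units (assumption: SD not given):

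detectable difference = (z for two-sided α + z for 80% power) × √(2/n)

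- n = 30, α = 0.05: (1.960 + 0.842) × 0.2582 = 0.72 SD
- n = 27 (the protocol's 10% practitioner loss), α = 0.05: 2.802 × 0.2722 = 0.76 SD
- n = 30, α = 0.025: (2.241 + 0.842) × 0.2582 = 0.80 SD
- n = 27, α = 0.025: 3.083 × 0.2722 = 0.84 SD

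Power for a 0.5 SD difference with 30 per arm is 49% at α = 0.05 and 38% at α = 0.025. Four cues and two device arms give 8 contrasts. The 0.05 figures make no allowance for multiplicity, and the 0.025 figures allow only for the two device arms.

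**The case against.** A reader might infer that the secondary objective in Section 3.1 cannot be answered at all. The documents do not support that. The objective asks whether the factors used change, not what weight a device reading receives. All arms complete both vignette rounds, randomisation falls between them, and the Précis states the intention to look at pre/post differences. The four contributions estimated under 11.3 are the quantities to compare. The clinical data bear on the objective too: lesion features and treatment are recorded in both phases, and the device is used in the intervention phase.

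A second objection is that a cue × period × arm term is detail for a statistical analysis plan, which is not shown. In part this stands: the absence of a written model term would not be a finding by itself, and no sentence forbids the contrast. But 11.3 does more than stay silent. It names within-equation tests as the main a priori hypotheses, and those do not address change relative to control. No analysis plan can supply a device reading that was never shown in the vignettes.

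Third, no text says that significance before and non-significance after would be taken as a device effect. That is correct, and Step 4 shows only why such a reading would be unsafe. A nomothetic equation is also already planned, so pooling itself is not new.

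Finally, the reinforce-or-override claim is a single clause in the rationale and appears in neither the objectives nor the outcomes. This limits its weight but does not remove the mismatch.

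**Conclusion.** The point holds in a limited form. The vignettes as described cannot show how device information is weighed against color, luster, roughness and risk, so the clause in Section 2.2 promises more than the instrument can deliver. They can show whether the four cue weights shift after device experience, that is, carry-over into decisions made without a reading. The vignette tests stated in 11.3, read with the before/after framing in the Précis and Section 3.2.2, do not separate such a shift from a retest effect common to all arms.

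The contrast that would do so is available from data already planned, but it is coarse. About 0.72 SD of practitioner-level change is detectable with 30 per arm, and 0.76 SD with 27 (80% power, two-sided 0.05). These figures assume one change score per practitioner, a normal approximation and no allowance for multiplicity. The primary outcomes are unaffected. The change should be made, because it concerns what a secondary aim can claim and costs almost nothing.

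**What to change.** 1. In Section 11.3, make the main vignette test a pooled (nomothetic) model of the responses with cue × period × arm terms, clustered on practitioner. For each cue, report the change in weight in each device arm minus the change in the no-device arm, with a confidence interval. Keep the within-equation significance and explained variance as description.
2. Keep the same four-cue vignettes in all arms and both rounds. A device reading should not be added to the device arms' post-study vignettes alone. The instrument would then differ between arms in the second round only, and the contrast in item 1 would be confounded with the changed content.
3. In Section 2.2, limit the claim to change in the weights of the four cues and delete the statement about device information reinforcing or overriding them.

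The cost is wording and analysis programming only, with no new data and no extra practitioner time. The downsides are that the study gives up the claim about how a device reading is weighed, and that only large shifts in cue weights will be detectable. The report should say so, so that a null result is not read as evidence of no change.

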7.2 Questionnaire Administration

Practitioner: Practitioners will be directed to a secure website to complete the pre-and poststudy vignettes. After providing consent, practitioners will observe 16 unique patient profiles consisting of a text vignette and photo of a SOCL. The 16 profiles have been shown to be a valid and reliable approach to examining how practitioners use patient demographic cues to make lesion management decisions. For each patient profile, practitioners read a clinical vignette that describes the patient as having 4 various cues (color, luster, roughness of the lesion and caries risk characterization).

All practitioners will complete a post study questionnaire. This will also be done electronically similar to the vignettes. Practitioners randomized to the device arm will complete a post-study questionnaire on the utility and value of their device in addition to the pre-and post-study vignettes while practitioners on the no device arm will complete a post-study questionnaire on the vignette and participation in the study.

Patient: The patient will complete the demographics form.

8 ASSESSMENT OF SAFETY

8.1 Specification of Safety Parameters

Safety monitoring for this study will focus on unanticipated problems involving risks to participants, including unanticipated problems that meet the definition of a serious adverse event.

8.1.1 Unanticipated Problems

The Office for Human Research Protections (OHRP) considers unanticipated problems involving risks to subjects or others to include, in general, any incident, experience, or outcome that meets **all** of the following criteria:

- Unexpected in terms of nature, severity, or frequency given (a) the research procedures that are described in the protocol-related documents, such as the IRB-approved research protocol and informed consent document; and (b) the characteristics of the subject population being studied;
- Related or possibly related to participation in the research (possibly related means there is a reasonable possibility that the incident, experience, or outcome may have been caused by the procedures involved in the research); and
- Suggests that the research places subjects or others at a greater risk of harm (including physical, psychological, economic, or social harm) than was previously known or recognized.

8.1.2 Serious Adverse Events

A serious adverse event (SAE) is one that meets one or more of the following criteria:

- Results in death
- Is life-threatening (places the subject at immediate risk of death from the event as it occurred)
- Results in inpatient hospitalization or prolongation of existing hospitalization
- Results in a persistent or significant disability or incapacity
- Results in a congenital anomaly or birth defect

An important medical event that may not result in death, be life threatening, or require hospitalization may be considered an SAE when, based upon appropriate medical judgment, the event may jeopardize the subject and may require medical or surgical intervention to prevent one of the outcomes listed in this definition.

8.2 Reporting Procedures

Incidents or events that meet the OHRP criteria for unanticipated problems require the creation and completion of an unanticipated problem report form. OHRP recommends that investigators include the following information when reporting an adverse event, or any other incident, experience, or outcome as an unanticipated problem to the IRB:

- Appropriate identifying information for the research protocol, such as the title, investigator's name, and the IRB project number;
- A detailed description of the adverse event, incident, experience, or outcome;
- An explanation of the basis for determining that the adverse event, incident, experience, or outcome represents an unanticipated problem;
- A description of any changes to the protocol or other corrective actions that have been taken or are proposed in response to the unanticipated problem.

To satisfy the requirement for prompt reporting, unanticipated problems will be reported using the following timeline:

- Unanticipated problems that are serious adverse events will be reported to the IRB and to NIDCR within 1 week of the investigator becoming aware of the event.
- Any other unanticipated problem will be reported to the IRB and to NIDCR within 2 weeks of the investigator becoming aware of the problem.
- All unanticipated problems should be reported to appropriate institutional officials (as required by an institution's written reporting procedures), the supporting agency head (or designee), and OHRP within one month of the IRB's receipt of the report of the problem from the investigator.

All unanticipated problems will be reported to NIDCR's centralized reporting system via Rho Product Safety:

- Product Safety Fax Line (US): [name]
- Product Safety Fax Line (International): [contact]
- Product Safety Email: [contact]

General questions about SAE reporting can be directed to the Rho Product Safety Help Line (available 8:00AM – 5:00PM Eastern Time):

- US: [name]
- International: [contact]

